10.4. Care Procedures After Injection

To evaluate the subject for possible immediate immunological AEs, the subject will remain in direct observation of medical personnel who are skilled in the management of an allergic reaction for 30 minutes after receiving the injection of study drug and until the subject exhibits no sign of an immunological or other clinically significant systemic or local AE. The subject's vital signs should be stable before the subject can leave direct observation (see section 14.9).

The Investigator or qualified designee will then apply a sterile dressing to the injection areas with hypoallergenic tape. The subject will be instructed to remove the dressing in the evening.

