3.1.9. Adverse Events

Medically significant changes that occur after enrollment into this study are recorded as adverse events (AEs).

The following information is collected for all AEs:

- Verbatim description
- Date of Onset
- Date of Resolution /or Ongoing
- Severity (Mild, Moderate, Severe)
- Relationship to Study Drug (Not Related, Unlikely related, Possibly related, Probably related)
- Action taken with study drug (None, Drug Interrupted, Drug Withdrawn)
- Outcome (Recovered/Resolved, Recovered/Resolved w/Sequelae, Recovering/Resolving, Not Recovered/Not Resolved, Fatal, Unknown)
- Whether the AE led to study discontinuation
- Whether or not a concomitant medication or procedure was required
- Classified as a serious adverse event (SAE) or not
- SAE Code (Death, Life-threatening, Inpatient or prolonged hospitalization, Persistent or significant disability/incapacity, Congenital anomaly or birth defect, Other medically important event)
- Adverse event of special interest (Yes/No)

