3.1.13. Vital Signs

Blood pressure (systolic/diastolic), respiratory rate, pulse rate, and body temperature will be assessed at each study visit. On injection days (Day 1, Day 22, and Day 43), blood pressure, respiratory rate, and pulse rate will be measured prior to the injections (up to 4 hours prior to the injection), and at 15 and 30 minutes after the injection. On injection days, body temperature will be taken only prior to the injection, and at the 30-minute post-dose measurement. On injection days, the time vital signs are taken will also be recorded.

3.1.14. 12-Lead Electrocardiogram

During the screening period, subjects will have a resting 12-lead ECG. A qualified physician will assess the ECG to normal, abnormal not clinically significant, or abnormal clinically significant. The investigator will be able to record any comments regarding the ECG, such as explaining any abnormal findings or providing details if the ECG was not done per protocol.

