3.2.6.1.1. Adverse Event Treatment Session

An AE's association with a treatment session will be based on the start date of AEs compared to the date of the injection. Adverse events with a start date between the Day 1 visit date and the day prior to the Day 22 visit date will be associated with Treatment Session 1. AEs with a start date between the Day 22 visit date and the day prior to the Day 43 visit date will be associated with Treatment Session 2. AEs with a start date between the Day 43 visit date and the Day 180 (EOS/ET) visit date will be associated with Treatment Session 3.

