3.4.7.1. Adverse Events

The following listings will be provided based on all AEs:

- Listing of AEs
- Listing of deaths
- Listing of SAEs
- Listing of AEs leading to discontinuation

The following summary tables of AEs will be presented by assigned region (buttock or thigh) and overall:

- Treatment-Emergent AEs
 - Overall summary
 - By preferred term

- By preferred term and severity
- By frequency for SAEs
- By frequency for most common non-serious AEs
- Treatment-Related AEs
 - Overall summary
 - By preferred term
 - By preferred term and severity
 - By preferred term and treatment session
 - Duration of AEs

The overall summary will consist of the following items:

- Total number of AEs
 - All AEs
 - Mild AEs
 - Moderate AEs
 - Severe AEs
- Total number of subjects with
 - At least one AE
 - At least one SAE
 - At least one severe AE
 - At least one AE leading to discontinuation
- Total number of subjects who died (Treatment-emergent only)

Percentages for the total number of mild, moderate, and severe AEs will be based on the total number of all AEs in the corresponding assigned region and overall.

The by frequency summaries will also include the total number of occurrences the AE preferred term was reported as well the number of subjects with at least one report of the AE. Most common non-serious AEs are any preferred term AE that at least 5% of the subjects report at least once.

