3.5.3. Imputation of Partial Dates

Study visit dates, birthdates, informed consent date, injection dates/times, all assessment dates, all lab dates, and date of completion/last contact date must be complete dates; no imputations will be done. No imputations will be done for partial medical history onset/resolution dates (except EFP onset date), partial alcohol/tobacco stop dates, partial AEs onset/end dates and partial concomitant medication start/stop dates. All AEs with a missing onset day will be considered treatment emergent except if the onset month/year is prior to the first injection date. All medications with a missing onset and stop day will be considered concomitant except if the stop month/year is prior to the first injection date.

For EFP onset date and prior EFP medications/treatment dates, missing EFP onset dates or missing prior EFP medication/treatment start dates will be imputed with the 1st day of the month and missing onset month will be imputed with January. If the EFP onset date is indicated as completely unknown but starting less than 5 years ago, the EFP onset date will be imputed as the informed consent date minus 5 years. If the EFP onset date is indicated as completely unknown but starting more than 5 years ago, the EFP onset date will not be imputed. Missing EFP medication/ treatment end days will be imputed with the last day of the month and missing end

months will be imputed with December, except if the end year is equal to the date of injection year and then the EFP medication/treatment end date will be imputed with the first injection date.

All the missing date imputation will be used for the summary tables only; no imputation will be applied for the subject listings.

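### AE onset is recorded as a date without a time, so events that begin during the post-injection observation cannot be separated from other events on the same injection day

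*Protocol*

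**What the plan says.** - **Observation.** Protocol 10.4 gives its purpose as "To evaluate the subject for possible immediate immunological AEs, the subject will remain in direct observation of medical personnel". It lasts "for 30 minutes after receiving the injection of study drug and until the subject exhibits no sign of an immunological" or other clinically significant AE remains, so 30 minutes is a minimum.
- **Times that are collected.** SAP 3.1.13: "On injection days, the time vital signs are taken will also be recorded". SAP 3.5.3 lists "injection dates/times, all assessment dates" among the items that must be complete.
- **AE record.** SAP 3.1.9 lists what is collected for every AE. Onset is a date; neither a time nor an indicator of onset under observation is listed. There is a flag, "Adverse event of special interest (Yes/No", but the special-interest terms are redacted. SAP Table 8 derives onset day and duration in whole days.
- **Link to a session.** SAP 3.2.6.1.1: "An AE's association with a treatment session will be based on the start date of AEs compared to the date of the injection". The injection date is included. Session 2, for example, takes "AEs with a start date between the Day 22 visit date and the day prior to the Day 43 visit date".
- **Treatment-emergent.** SAP 3.2.6.1 counts any AE dated on or after the first injection date.
- **Tables.** SAP 3.4.7.1 plans a table "By preferred term and treatment session", listed under treatment-related AEs only. SAP 3.4.7.1.2 summarises AEs of special interest by region and overall, with no split by session or timing.

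**The concern.** Safety is the primary objective. Protocol 10.3 calls the product a foreign protein, and Protocol 8.1.3 reports that all treated women in earlier work had antibodies after three treatment visits. Whether immediate reactions become more frequent from the first to the third session is therefore a natural question for this trial, and Protocol 10.4 puts staff in place to see such reactions.

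The clock times of injection and vital signs are kept. The one missing link is the time of AE onset. Without it, three different situations share one date: an event present before the injection, an event seen under observation, and an event at home that evening. The first bears on whether the event is treatment-emergent and on its session. The second is what the observation is meant to find.

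**Working it through.** The plan states no figure on this point, and the sample size (up to 150) comes with no event rate or precision target. The check is therefore mainly logical.

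**1. Apply the SAP's date rules to injection-day AEs.**

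| True onset | Treatment-emergent (SAP 3.2.6.1) | Session (SAP 3.2.6.1.1) | What the true timing implies |
|---|---|---|---|
| Day 1, before injection | Yes | 1 | Precedes first dose; no session |
| Day 1, under observation or later | Yes | 1 | Same as SAP |
| Day 22, before injection | Yes | 2 | Treatment-emergent, session 1 |
| Day 22, under observation or later | Yes | 2 | Same as SAP |
| Day 43, before injection | Yes | 3 | Treatment-emergent, session 2 |
| Day 43, under observation or later | Yes | 3 | Same as SAP |

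Pre-injection events are misplaced: on Day 1 in treatment-emergent status, on Days 22 and 43 in session. Such events can be on record, because Protocol 14.5.1 collects AEs from consent. Protocol 17.6.4 also requires that the event was not present before the first dose; on Day 1 a date cannot settle that. Events under observation are placed in the right session but merged with later same-day events.

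**2. Compare with SAP Table 8.** Table 8 defines treatment-emergent as starting after the first dose, and the session as the one preceding the onset date. Read strictly on dates, a Day 1 AE is not treatment-emergent and has no session, a Day 22 AE goes to session 1, and a Day 43 AE to session 2. For AEs on Days 2, 23 and 44 the two sets of rules agree. In this check they part only on the injection dates, where immediate reactions fall.

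**3. No same-day allergic-type AE.** Every AE that begins under observation carries the injection date. If no allergic-type AE is dated on an injection day, none began under observation. The one-sided 95% upper limit for zero events in n is 1 − 0.05^(1/n):
- per woman, n = 150: 1 − 0.05^(1/150) = 1.98%;
- per session, n = 150 × 3 = 450: 1 − 0.05^(1/450) = 0.66%.

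Both limits follow from dates alone. The second assumes that all sessions are given and are independent.

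**4. Some same-day allergic-type AEs.** If k of n women injected in a session have one, the number with onset under observation lies between 0 and k, and the proportion between 0 and k/n. With n = 150, each such woman widens the range by 1/150 = 0.67 percentage points. With k1 such women in session 1 and k3 in session 3, the change in the count under observation can be anything from −k1 to +k3, so even its direction is open. The documents give no rate from which to predict k.

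**The case against.** The strongest reply is that the plan already captures most of this. Injection-day AEs are assigned to that day's session, and a reaction judged possibly or probably related, or with relationship missing, enters the by-session table. Vital signs at about 15 and 30 minutes are timed and summarised as change from that day's pre-injection value (SAP 3.4.7.4). Causality assessment helps to set aside pre-injection events. Protocol 10.4 is a care and discharge procedure, not an endpoint. The eCRF and the table shells are not in the documents.

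Much of this stands, and it rules out three stronger readings that a reader might infer:
- *Reactions cannot be counted by session.* SAP 3.2.6.1.1 and 3.4.7.1 contradict this.
- *The observation yields no result.* The vital signs are summarised, and AEs and local reactions recorded after injection at each treatment visit enter the AE data.
- *A zero result could not be reported.* Step 3 shows that it could.

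The substitutes do not close the remaining gap. Vital signs miss a reaction that leaves them unchanged. The by-session table depends on the causality judgement. The special-interest flag has unknown coverage, and its table has no session split. Preferred term plus date is ambiguous for terms such as injection site pruritus (11.1%), swelling (7.4%) and erythema (2.1%), all reported as treatment-related in the phase 2b study (Protocol 8.3): the date does not show whether onset came within minutes or hours later.

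**Conclusion.** The point holds in a limited form. As specified, the AE data cannot separate onset before injection, under observation and later on the same injection day. When same-day events occur, a per-session count restricted to the observation period cannot be produced. An AE that began before injection on Day 1 is counted as treatment-emergent, and one that began before injection on Day 22 or 43 is assigned to that day's session.

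The size depends on how many same-day allergic-type events occur, which the documents do not let one predict. With none, nothing is lost and the limits of 1.98% and 0.66% can be stated. With k, the uncertainty is 0 to k. The length of the observation as a share of the day is not a measure of the problem, because reactions to an injection are not spread evenly over 24 hours.

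This rests on SAP 3.1.9 being a full account of the AE fields, on complete AE start dates (SAP 3.5.3 does not impute partial ones), and on an agreed list of allergic-type terms. It is a cheap improvement, not a flaw that undermines the safety analysis.

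**What to change.** - **Data.** For AEs starting on an injection day only, add to the eCRF and SAP 3.1.9 an onset time or a three-way item: before injection / during post-injection observation / later that day. The three-way item suits an observation period of variable length. State where an onset between the first and last injection of the visit belongs.
- **Derivation.** Use the item in SAP 3.2.6.1 and 3.2.6.1.1 to set treatment-emergent status on Day 1 and the session on Days 22 and 43. Bring the wording of Table 8 into line.
- **Table.** In SAP 3.4.7.1 add one table of TEAEs with onset during observation, by preferred term and session, with the women injected in that session as denominator. Show hypersensitivity-type terms separately from local injection-site terms. Otherwise bruising and pain (75.1% and 59.3% treatment-related in the phase 2b study) would probably dominate it.

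The cost is one item for a subset of AEs, one short table, and minor data entry. Subjects are already under observation, so no visit or procedure is added.

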10.5. Discussion of Study Design, Including the Choice of Control Groups

The design of this study was based on the primary objective to assess the safety of EN3835 0.84 mg per treatment area in the concurrent treatment (total dose of 1.68 mg) of EFP in a treatment region (bilateral buttocks or bilateral posterolateral thigh) in adult women. It is an open-label study.

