A recent Phase 2b, randomized, double-blind, placebo-controlled study (EN3835-201) of 375 women randomized to treatment of one treatment area (quadrant) (quadrant was defined in study EN3835-201 as a left buttock, a right buttock, a left posterolateral thigh or a right posterolateral thigh) of cellulite with EN3835 0.84mg or placebo in a 1:1 ratio assessed the effectiveness and safety of EN3835. Efficacy in this study was evaluated based on cellulite assessments using the Clinician Reported Photonumeric Cellulite Severity Scale (CR-PCSS), Patient Reported Photonumeric Cellulite Severity Scale (PR-PCSS), Investigator Global Aesthetic Improvement Scale (I-GAIS), Subject Global Aesthetic Improvement Scale (S-GAIS), and Subject Satisfaction with Cellulite Treatment.

Results from the Phase 2b study demonstrated that treatment (3 visits approximately 21 days apart) improved the cellulite severity of the treated quadrant as assessed by the primary endpoint of 2-level composite responder analyses, the proportion of responders based on an improvement of ≥ 2 level in the appearance of cellulite in both the patient PR-PCSS and the clinician CR-PCSS of buttocks and thighs was statistically significantly greater in subjects who received EN3835 0.84 mg (10.6%; $p < 0.001$) compared to subjects who received placebo (1.6%); 1-level (or greater) responders in the PR-PCSS of EN3835-treated subjects (72.3%) was significantly

greater than 1-level responders in the placebo group (51.6%) ($p < 0.001$); statistically significant ($p \leq 0.001$) improvement in the appearance of cellulite based on the subject S-GAIS were observed in EN3835 0.84-mg group (73.1%) compared to the placebo group (44.0%); and sixty-two percent (62.9%) of subjects in the EN3835 0.84mg group were satisfied or very satisfied with the results of their cellulite treatment compared with only 35.9% of subjects in the placebo group ($p < 0.001$). In subjects treated in buttocks ($n = 187$), the proportion of 2-level composite responders was statistically significantly greater in subjects who received EN3835 0.84 mg (14.9%; $p < 0.001$) compared to subjects who received placebo (1.1%); 1-level (or greater) responders in the PR-PCSS of EN3835-treated subjects (72.7%) was significantly greater than 1-level responders in the placebo group (47.8%) ($p < 0.001$).

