8.3. Summary of Known Risks and Benefits

A summary of safety risks is provided in the IB.⁽¹¹⁾ The following events have been commonly observed: local injection site reactions (injection site bruising, injection site swelling, and injection site pain) for the various approved indications as well as those being investigated. In the phase 2b study of EN3835 in women with EFP, the following treatment-related adverse events $\geq 2\%$ of 189 EN3835-treated women were reported: injection site bruising (75.1%), injection site pain (59.3%), injection site nodule (14.3%), injection site pruritus (11.1%), injection site swelling (7.4%), injection site induration (5.8%), injection site mass (5.3%), injection site discoloration (3.2%), and injection site erythema (2.1%). These events are similar to events reported in the clinical trials of EN3835 for the approved indications. Post-marketing safety data have been consistent with data reported in clinical trials.

Although a thorough benefit of EN3835 has not been fully evaluated in the treatment of EFP, the efficacy results from the Phase 2b study and previous EFP studies warranted further development.

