9. OBJECTIVES

9.1. Primary Objective

The primary objective of this study is to assess the safety of EN3835 in the treatment of edematous fibrosclerotic panniculopathy (EFP) commonly known as cellulite in adult women.

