3.1.3.2. Study Drug Administration

A dose of 0.84 mg of EN3835 per treatment area will be administered as 12 subcutaneous injections (0.3-mL injection administered as three 0.1-mL aliquots per injection) in each of two treatment areas for a total dose of 1.68 mg and a total volume of 7.2 mL (3.6 mL per treatment area). Total number of injections will be 24 injections per treatment visit into the assigned region (left and right buttocks or left and right posterolateral thighs). There will be 3 treatment visits at 21-day intervals, ie, treatments on Days 1, 22, and 43 will be administered.

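### Injection-site reactions have no specified by-area recording or summary, so the planned per-woman rates only bound the reaction rate per treated area

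*Protocol*

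**What the plan says.** - **Purpose.** Protocol 10.5 says that the design follows from the "primary objective to assess the safety of EN3835 0.84 mg per treatment area in the concurrent treatment (total dose of 1.68 mg"). The formal objective in Protocol 9.1 is more general: "The primary objective of this study is to assess the safety of EN3835 in the treatment of edematous fibrosclerotic panniculopathy (EFP").
- **Treatment here.** Both areas of one region are injected: "Total number of injections will be 24 injections per treatment visit into the assigned region" (SAP 3.1.3.2).
- **Earlier rates.** Protocol 8.1.3 describes the Phase 2b study as "375 women randomized to treatment of one treatment area (quadrant"). Protocol 8.3 gives its treatment-related events: "of 189 EN3835-treated women were reported: injection site bruising (75.1%), injection site pain (59.3%), injection site nodule (14.3"%), followed by less common reactions.
- **Adverse event items.** Under "The following information is collected for all AEs", SAP 3.1.9 lists a verbatim description, dates, severity, relationship and other items. None is a side or treatment area.
- **Adverse event tables.** SAP 3.4.7.1: "The following summary tables of AEs will be presented by assigned region (buttock or thigh) and overall". In the preferred-term tables a woman counts once per term (SAP 3.4.7.1.1). Some event counts are also planned, but none by left or right area.
- **Where the area is used.** Exposure is summarised for each side (Protocol 17.6.2, SAP 3.4.7.2), and a CR-PCSS responder is defined for a treatment area (SAP 3.2.5.3).
- **Local tolerability.** The Schedule of Events has a row for local reactions and tolerability in the assigned areas, separate from the adverse event row. No SAP section analyses it by area.

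**The concern.** What differs from Phase 2b is that two areas are treated at the same visit. A woman with two treated areas has two opportunities for each local reaction, so her chance of at least one can rise even when the risk in each area has not changed. A table that counts women cannot tell that arithmetic effect from a higher risk per area. A per-woman rate equal to Phase 2b is ambiguous too, because it is compatible with a lower rate per area.

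The duration table has a related gap. SAP 3.4.7.1.1 adds up the durations of events with the same term in one treatment session. No rule says whether a reaction on both sides is one event or two, so two reactions running side by side could be counted as one of twice the length.

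**Working it through.** **Inputs**
- Phase 2b, one area per woman, n = 189 (Protocol 8.1.3 and 8.3): bruising 75.1%, pain 59.3%, nodule 14.3%, pruritus 11.1%, swelling 7.4%.
- This study: two areas per woman, up to 150 women (Protocol 17.1).
- Correlation ρ between a woman's two areas: not in the documents. It is assumed to lie between 0 (independent) and 1 (both sides always react together).

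**The plan's own figures.** The dose reproduces: 12 × 0.07 mg × 2 areas = 1.68 mg. The percentages are whole counts out of 189: 142, 112, 27, 21 and 14. The plan gives no error rate, power or margin for the 150, so there is no sample-size calculation to reproduce.

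**Per-woman rate at unchanged per-area rate p**

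P(at least one side reacts) = 1 − [(1 − p)² + ρ·p·(1 − p)]

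At ρ = 1 this is p. At ρ = 0 it is 1 − (1 − p)². For nodule, p = 27/189 = 0.1429:
- ρ = 0: 1 − 0.8571² = 1 − 0.7347 = 26.5%
- ρ = 0.5: 1 − (0.7347 + 0.5 × 0.1429 × 0.8571) = 1 − 0.7959 = 20.4%
- ρ = 1: 14.3%

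| Reaction | ρ = 1 (equals Phase 2b) | ρ = 0.5 | ρ = 0 | Largest ratio to Phase 2b |
|---|---|---|---|---|
| Bruising | 75.1% | 84.5% | 93.8% | 1.25 |
| Pain | 59.3% | 71.3% | 83.4% | 1.41 |
| Nodule | 14.3% | 20.4% | 26.5% | 1.86 |
| Pruritus | 11.1% | 16.0% | 21.0% | 1.89 |
| Swelling | 7.4% | 10.8% | 14.3% | 1.93 |

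**The reverse reading.** An observed per-woman rate Q gives a per-area rate between 1 − √(1 − Q) at ρ = 0 and Q at ρ = 1. A bruising rate of 75.1% fits 50.1 to 75.1% per area. A nodule rate of 14.3% fits 7.4 to 14.3%.

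**How it could look beside Phase 2b** (illustration only; the plan has no such test). For nodule with no change in per-area risk:
- ρ = 0: 40/150 against 27/189, Fisher p = 0.0058
- ρ = 0.5: about 31/150 against 27/189, Fisher p = 0.15

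So an apparent difference from the number of areas alone needs a correlation near the independent end.

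**Duration rule.** Left and right bruising of 10 days each, entered as two events in one session, sum to 20 days and fall in the 15-to-21-day class. Entered as one bilateral event, they last 10 days and fall in the class above 7 and up to 14 days.

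**The case against.** A reader might infer that side is not recorded at all, that this study cannot be compared with Phase 2b, or that the safety objective goes unanswered. The documents do not support any of these.

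- **Recording.** The list in SAP 3.1.9 is not the eCRF, which is not among the documents. Local reactions are assessed in the assigned areas at treatment and follow-up visits, and a verbatim term may name a side. The table shells are in a separate SAP module. What is shown is that no item for side is listed and no by-area summary is specified.
- **Unit of counting.** Not every planned output counts women. SAP 3.4.7.1 includes total events and occurrences per term, and SAP 3.5.2 builds a by-event dataset.
- **Comparison.** No comparison with Phase 2b is planned. The per-woman, treatment-related table has the same unit as the rates in Protocol 8.3. A comparison can be made, but it is confounded by the number of areas.
- **Rationale.** Protocol 8.4 and 10.2 support two-area treatment by local findings, local activity and the absence of quantifiable systemic exposure, not by comparing rates. Protocol 8.1.3 also reports an earlier Phase 1 study that treated two areas at once.
- **Objective.** Protocol 9.1 has no per-area element, and in 10.5 the words about area can be read as describing the dose. Per-woman incidence properly describes what a woman treated on both sides experiences.
- **Correlation.** Both sides share the woman, the drug and the visit, so full independence is an extreme case.

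All of this stands, and it limits the point. It does not supply a by-area summary. If the argument for treating two areas is that effects are local, the rate per area is the direct description of it, and optional verbatim text is not a reliable source for side.

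**Conclusion.** The point holds as a specific, inexpensive improvement and not as a failure of the primary objective. The planned outputs measure the total burden of concurrent treatment validly, but they only bound the per-area rate. For the less common reactions the bounds differ by almost a factor of two (nodule 14.3 to 26.5% per woman at unchanged per-area risk); the ratio is at most 1.41 for pain and 1.25 for bruising. These ranges assume a left-right correlation between 1 and 0 and both areas treated in every woman.

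Recording side would let the per-area rate be estimated directly, without a correlation assumption. It would not show that a difference from Phase 2b is due to giving 1.68 mg at once: that would remain a comparison of an open-label single arm with the active arm of a double-blind study. The duration ambiguity exists whether or not anyone makes that comparison.

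**What to change.** 1. Add one item to SAP 3.1.9, and to the eCRF if it is not already there, for each injection-site event: left, right or both. Capture it prospectively.
2. In SAP 3.4.7.1 add one descriptive table of treatment-related, treatment-emergent injection-site events by preferred term and region, with injected treatment areas as the denominator and intervals that allow for two areas per woman. Place it beside the per-woman table. Treatment-related events are the ones that match Protocol 8.3.
3. Footnote that per-woman rates are not like-for-like with the single-area Phase 2b rates, and that any such comparison is cross-study and descriptive.
4. In SAP 3.4.7.1.1 state whether a bilateral reaction is one event or two, and that its concurrent left and right durations are not added together.

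The cost is slightly more data entry and one more table. The sample size and the visits do not change.
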